## D. Preliminary Studies/Progress Report

**Pediatric viral suppression at FACES:** Drs. [name], multiple-PI on this proposal, [name], co-investigator, and colleagues have assessed prevalence of treatment failure amongst children undergoing routine VL testing at FACES sites between June 2014–May 2015. Among 1190 children and young adolescents 0-14 years of age undergoing routine VL testing, 748 (63%) were virologically suppressed. In multivariable analysis, unsuppressed children were more likely to be male (adjusted odds ratio (aOR) 2.1, 95% Confidence Interval (CI) 2.1-3.6) and have had an ART regimen change (aOR 2.0, CI 1.0-3.7) than suppressed children. A third of children with virologic failure never had a follow-up viral load. Among those that did, VL suppression was only achieved by 23% versus 93% among those suppressed at baseline ( $p<0.0001$ ). Mean time for a follow-up VL in children with virologic failure was 11.3 months (95% CI 9.5-13.2).

[figure not shown]
Table 2. Patterns of HIV DRMs among children and adolescents in Kenya, 2013	
Specific mutations with VL <math>\geq</math> 1000 copies/mL	N (%) (n=136)
NRTI, any	108 (79%)
M184V	103 (75%)
K65R	6 (4%)
1 TAM	13 (10%)
2 TAMs	7 (5%)
3 TAMs	15 (11%)
L74V	36 (27%)
NNRTI, any	117 (86%)
K103N	46 (34%)
Y181C	43 (32%)
G190A/C	39 (29%)
PIs, any	0
Any mutations	121 (89%)

**National drug resistance surveillance for children in Kenya:** In 2013, [name], site-PI on this proposal, led the National AIDS and STI Control Programme's (NASCOP) cross-sectional, nationally-representative survey of acquired HIV DRMs among adults and children on ART for at least 12 months in Kenya. Virologic failure was defined as a VL  $\geq$ 1000 copies/mL per national guidelines and 90% of the children were on a NNRTI-containing regimen. Overall, 31% of the 461 children had virologic failure, as compared to only 11% of the adults. Of the children with virologic failure, 89% had at least one DRM detected. Seventy-nine percent had DRMs to NRTIs, 86% to NNRTIs, 77% to both NRTIs and NNRTIs, and 0% to PIs (though PI use was infrequent in this cohort). The most common DRMs were M184V and L74V for NRTIs and K103N, Y181C, and G190A for NNRTIs (Table 2). In addition to conducting this survey, [name] was involved in training and capacity building of providers in handling DRM testing results and results dissemination.

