**HIV DRM testing:** We will conduct targeted HIV DRM testing at the Kisumu-based KEMRI-CDC HIV Research laboratory using consensus sequencing on all plasma samples which lack viral suppression, defined as VL  $\geq$  1000 copies/mL per national guidelines. “Targeted” DRM testing will include DRM testing for each child on the first detection of such a VL and in children newly initiating ART. Subsequent samples from the same child on the same ART regimen will not be routinely retested, since costs of repeat DRM testing outweigh detection of new DRMs. Since approximately 65% of children achieve viral suppression currently in the FACES-supported facilities, including the study facilities, i.e. 35% have viremia VL  $\geq$  1000 copies/mL, we anticipate conducting DRM testing in at least 100 samples in participants in the intervention arm over the course of this pilot study. Such plasma samples, once processed from whole blood within 6 hours of collection, will be transported from the local health facility to the KEMRI-CDC laboratory the same day.

To conduct the HIV DRM testing, we are partnering with KEMRI-CDC, which has extensive facilities, including the HIV Research Laboratory led by [name], a collaborator on this proposal, located immediately outside of Kisumu. The KEMRI-CDC HIV Research laboratory utilizes Applied Biosystems (ABI) 3130x/ Genetic Analyzers to conduct its HIV drug resistance testing on 0.5-1mL of plasma. These analyzers have all steps automated, from polymer loading to sample injection to data analysis. This laboratory utilizes an optimized in-house assay to detect reverse transcriptase- and PI-based mutations. This validated, assay is broadly sensitive in genotyping HIV-1 subgroups, detecting all mutations classified in the IAS-USA mutations list, and more sensitive than commercially available assays for mixed viral populations. The KEMRI-CDC in-house assay can run samples from plasma or DBS; the ability to also use DBS is a key asset for our study, in case adequate volume of plasma cannot be obtained from our younger study population. DBS samples will be prepared by spotting 100  $\mu$ L of whole blood onto each of the preprinted circles on the DBS paper, then dried overnight at the local health facility at ambient temperature, and then transport wrapped DBS cards the next day.

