- a. Approximately 500uL of plasma from the samples genotyped by CS will be tested by staff at each facility trained in the use of OLA Simple, with oversight and assistance by the [name] team over a 3-week period. The facility staff performing OLA Simple and the [name] team will be "blinded" to CS results. Results from OLA Simple will be interpreted as presence or absence of resistance using test strip lines for each codon tested, based on a visual guide for test interpretation and automated analysis from captured test images. For OLA Simple tests that show INDETERMINATE results for one or more codons, samples will be re-tested for that codon in two separate kits; if the two new results concur, that result will be used, but if the two new sets do not concur the result will be reported as a test failure for that codon. (Specimens with indeterminate or discordant results will be further analyzed as noted in "d" below.)
- b. The OLA Simple results (MUTANT, WILD-TYPE, or INDETERMINATE at each codon) will be compared to sequencing results to calculate test sensitivity, specificity, indeterminate rate, and other parameters.
- c. OLA Simple will target specific NRTI, NNRTI, and PI DRMs, including: (1) NRTI M184V/I, K65R; (2) NNRTI K103N, Y181C, G190A, V106M; and (3) PI V82A, I50V/C, I54V/M/L, I84V/A mutations (based on published analysis of DRMs among Kenyan adults in the [name] laboratory using the Illumina platform^38).
- d. Prior studies have shown that OLA Simple may be more sensitive than CS; specifically, OLA Simple can detect DRMs at ~10% of a patient's viral population while CS detects DRMs at about ~20%. To address this sensitivity gap, any sample negative for DRMs by CS but positive by OLA Simple will be tested by the more sensitive Illumina sequencing (detects DRM down to 1% of viral population, requiring as few as 2000 copies of HIV RNA). Illumina sequencing will be performed in [name] laboratory in Seattle. To avoid shipping biohazardous material, we will ship non-infectious leftover RNA from OLA Simple testing in Kisumu.

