**Study Aim 2:** To estimate (**Aim 2a**) the effect of providing timely DRM results on viral suppression for intervention participants undergoing DRM, separately from the effect of POC alone, a secondary analysis will be performed with outcome of time to viral suppression. As in Aim 1, we will use a Cox model with primary predictor of intervention vs. control arm. To distinguish the effect of DRM results from that of POC VL testing, we will add a time-varying covariate which indicates, for each visit with a VL test, whether the clinician was notified of a positive DRM result since the child's prior VL test. If implemented as expected, all children without viral suppression will be provided DRM testing and providers notified of the results. This model will allow us to divide the estimated effect of the intervention between the effect of POC VL testing alone (on those who do not have DRM), and the effect of POC VL testing plus DRM testing for those who do undergo DRM testing. We will perform these Cox models both unadjusted and adjusted, accounting for other factors likely to affect viral suppression, particularly those that may vary at baseline in the intervention vs. control arms.

We will also describe the proportion of samples within the intervention arm that have any targeted DRMs by HIV drug classes, e.g. NRTIs, NNRTIs, and PIs. We will report the proportion of samples with each type of mutation detected by drug class, and further group these mutations into major and minor ones. For example, we will examine major mutations in M184V/I and K65R for NRTIs, K103N, Y181C, G190A, and V106M for NNRTIs, and V82A, I76V, 184V, L47A, L90M, M46I, and D30N for PIs; one or more of the NRTI and NNRTIs mutations alone accounted for 99% of the mutations detected among adults on 1st line ART from resource-limited settings with similar findings in small studies conducted with children, though the rates of PI-based mutations are increasing with more children on PI-based regimens. With 284 participants randomized to the intervention arm, we expect approx. 35% (100) to not achieve viral suppression at their 1st POC VL test and undergo DRM testing. With n=100, we will be able to estimate prevalence of DRMs to within +/- 5% to 10% of the 95% CIs. For example, for a class of DRMs with prevalence of 80%, we anticipate generating exact 95% CIs of 71.3%-87.0%; a less common DRM at 10% will generate 95% CIs of 5.1%-17.1%.

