We will use logistic regression models to identify risk factors associated with major and any DRMs. Potential risk factors of interest include individual-level (age, sex, duration on ART, prior antiretroviral exposure, prior viral suppression patterns, WHO clinical stage), clinical parameters (such as weight- or height-for-age), immunological status, family-level, HIV status of caregivers, socioeconomic status, and facility-level factors, such as volume of patients and urban/rural location. Covariates with p<0.20 in univariate analyses will be included in the multivariate models. We will also consider including interaction terms for any suspected effect modifiers such as age group of the child. The above analytic approaches will be taken for analyzing data from the NGS genotyping and phenotyping; in addition to descriptively generating the

patterns and distribution of NGS-detected DRM, including for minority variants and for mutations relevant to DTG, we will also compare them to the results obtained via CS when concurrent results are available.

To evaluate **Aim 2b**, CS and OLA simple-based DRM testing (Aim 4): To evaluate the test performance of OLA Simple (Aim 4a), we will compare test results for each codon from the OLA Simple test against a composite “gold standard” constructed from CS and Illumina sequencing (the latter performed on samples that are negative for DRMs by CS), stratified by retro- or prospective testing. We will calculate sensitivity, specificity, and positive and negative predictive values for the detection of DRMs per codon, organized by drug classes, for the OLA Simple. The above are the fundamental metrics the WHO, for example, considers in its prequalification application for in-vitro diagnostic and laboratory technologies approvals, achieving sensitivity and specificity >90% would demonstrate high test performance.

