### Risks to the Subjects

#### Human subjects involvement, characteristics, and design

Our proposed study design is an open-label randomized, controlled study piloting the use of POC VL testing and targeted DRM testing among HIV-positive children on ART age 1-14 years over a 12-month period in high-volume HIV treatment facilities in Kisumu, Kenya. At each facility, eligible children will be randomized 1:1 to either receive the intervention testing, consisting of quarterly POC VL testing and targeted DRM testing, or standard-of-care (SOC) testing based on the existing Kenyan national guidelines. We will follow the viral outcomes up to 24 months after enrollment for each child and compare VL suppression rates, defined as VL <1000 copies/mL by the Kenyan national guidelines, among intervention vs. control arms.

**Aim 1** of this study aims to determine the impact of point of care (POC) VL on the proportion of children achieving viral suppression and time to viral suppression for those who are either initiating ART or not suppressed.

The target population for aim 1 of the study includes approximately 700 HIV-infected children and young adolescents aged 1-14 years on ART at one of the intervention sites supported by FACES. Children who are outside of this age range will be excluded. These children will be randomized 1:1 to intervention vs. control arms. Therefore, approximately 350 children will receive the intervention (POC VL and DRM testing) and another 350 will receive the current standard of care as recommended by the Kenyan Ministry of Health, including routine viral load monitoring through centralized laboratory testing and DRM testing only for those failing 2nd line ART.

We conservatively estimate that around 90% of HIV infected children and adolescents and their families will agree to participate in the intervention portion of the study. Our sample size takes into account the potential for as much as 10% attrition due to loss to follow up, transfers out, or death based on current retention rates within the FACES program for children. Therefore, even if we experience as much as 10% attrition, we will still have a sufficient number of participants to evaluate the impact of the interventions.

**Aim 2** will explore the impact of targeted HIV drug resistance mutation (DRM) testing and patterns of DRM among HIV-infected children on ART without viral suppression.

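### The >90% benchmark for OLA Simple takes no account of how many positives or negatives a codon has, so for K65R and possibly the PI codons a pass would be uninformative

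*Protocol*

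**What the plan says.** Protocol section F (Data analysis and interpretation, Aim 2b) compares OLA Simple with a composite of consensus and Illumina sequencing. Sensitivity, specificity and predictive values are calculated "for the detection of DRMs per codon, organized by drug classes, for the OLA Simple", and the results are "stratified by retro- or prospective testing". The benchmark follows: "achieving sensitivity and specificity >90% would demonstrate high test performance". No interval, lower-limit rule, minimum number of positives or sample size goes with it.

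The target list in Study methods (OLA Simple-based DRM testing) is "1) NRTI M184V/I, K65R; (2) NNRTI K103N, Y181C, G190A, V106M; and (3) PI V82A, I50V/C, I54V/M/L, I84V/A mutations", which makes ten codon targets, four of them PI.

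On sample numbers, section F says "we expect approx. 35% (100) to not achieve viral suppression" at the first point-of-care test, out of 284 intervention children. Study methods puts it as a minimum: "we anticipate conducting DRM testing in at least 100 samples in participants in the intervention arm". The human subjects section uses a larger base: "approximately 350 children will receive the intervention". Study methods also adds stored, already-sequenced samples from the national reference laboratory, without giving a number.

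Section D (Preliminary Studies, Table 2) gives the mutation frequencies from the 2013 Kenyan survey of children with virologic failure. By class, the text reports "77% to both NRTIs and NNRTIs, and 0% to PIs".

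The SAP states that it covers Aims 1 and 2 but does not mention OLA Simple.

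**The concern.** An observed sensitivity means little without its denominator. For a codon with a handful of positives, the only result above 90% is a perfect score, and a mediocre assay reaches that often. A codon with no positives has no sensitivity estimate at all.

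The protocol's background section presents this work as a step in validating the assay for clinical use, on a path that includes WHO prequalification, and says that the PI codons have not yet been validated. Those are the codons for which a bare >90% is least informative. The protocol plans 95% intervals for the viral load assay comparison (Aim 1b kappa) and exact intervals for DRM prevalence (Aim 2a), so the gap is specific to OLA Simple.

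**Working it through.** **The plan's own figures.** 0.35 × 284 = 99.4, which gives the stated 100. The stated exact intervals for prevalence at n = 100 are 71.3–87.0% (at 80%) and 5.1–17.1% (at 10%). The mid-P exact method gives 71.3–87.0% and 5.2–17.1%, so they are reproduced to within 0.1 point. They concern prevalence only. The protocol states no precision for sensitivity or specificity.

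**Inputs.** N = 100 study samples (range: 0.35 × 350 = 122.5, about 123). Frequencies are from section D, Table 2 (n = 136).

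**Formulas.** Expected positives = N × frequency. With no misses among n results, the exact (Clopper–Pearson) two-sided lower 95% limit is 0.025^(1/n).

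| Codon | Survey | Positives in 100 | Best lower limit for sensitivity | Samples for 36 expected positives |
|---|---|---|---|---|
| M184V | 103/136 | 76 | 95.3% | 48 |
| K103N | 46/136 | 34 | 89.7% | 107 |
| Y181C | 43/136 | 32 | 89.1% | 114 |
| G190A (survey: G190A/C) | 39/136 | 29 | 88.1% | 126 |
| K65R | 6/136 | 4 | 39.8% | 816 |
| V106M | not given | unknown | – | – |
| PI, any | 0/136 | 0 | not estimable | – |

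**Smallest useful count.** 0.025^(1/35) = 89.997% and 0.025^(1/36) = 90.3%. So 36 is the smallest count whose two-sided lower limit can exceed 90%.

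**Larger study sample.** At N = 123 the expected positives are 42 (K103N), 39 (Y181C), 35 (G190A) and 5 (K65R). Only K65R stays far short.

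**Chance that a weak codon passes.** With 4 positives, only 4/4 exceeds 90%. If true sensitivity is 80%, the probability is 0.8^4 = 0.41. If it is 85%, it is 0.85^4 = 0.52.

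**PI codons.** The exact upper 95% limit for 0/136 is 1 − 0.025^(1/136) = 2.7%, so at most about 2.7 positives in 100 for the whole class at that limit. For a single PI codon with assumed prevalence p, the chance of no positives in 100 samples is (1 − p)^100: 61% at 0.5%, 37% at 1%, 13% at 2% and 0.6% at 5%.

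**Specificity.** K65R would have about 96 negatives, with best lower limit 0.025^(1/96) = 96.2%. M184V would have about 24, with best lower limit 0.025^(1/24) = 85.8%.

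**Two candidate rules tested.**
- Pooling by class: if all 75 of 75 M184V (the table's rounded 75%) and 2 of 4 K65R positives are detected, the NRTI class scores 77/79, with exact lower limit 91.2%. The class passes while K65R sensitivity is 50%.
- Requiring the lower limit to exceed 90%: M184V with 76 positives needs at least 74 detected. At a true sensitivity of 95% (the earlier result cited in the background) that happens in 26% of repeats. About 255 positives per codon would be needed for 80% power.

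**The case against.** The strongest reply is that the protocol sets no formal pass rule. It offers one benchmark sentence, does not say that a bare point estimate decides, does not require every codon to pass, and attaches no action to the result. That is correct. But the metrics are per codon, the sentence says what >90% would demonstrate, and nothing in the protocol or SAP limits it to codons with adequate counts.

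A second reply is that 100 is a floor and the reference laboratory samples come on top. This stands for K103N, Y181C and G190A: 7 to 26 further samples at the survey mix bring each to 36 expected positives, and a one-sided 95% limit would need only 29 positives. A reader might infer that most target codons will have too few positives. The documents do not support that, because the number and mix of the stored samples are not stated. K65R is different: at 4.4% it would need about 816 unselected samples.

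Third, the survey's PI zero comes from a cohort with infrequent PI use. The protocol says that PI mutations are increasing, and routine resistance testing is restricted to second- and third-line failures, so the stored samples may be richer in PI mutations. A reader might infer that there will be no PI positives. The documents support only that there may be none.

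Finally, this is a sub-aim of a pilot, and OLA Simple results go to neither patients nor providers. That limits the importance of the point but does not remove it.

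**Conclusion.** The concern holds in a limited form. As written, the benchmark can credit K65R, and any PI codon with only a few positives, with high performance on data that cannot show it. The three common NNRTI codons are borderline, and the documents do not settle whether they will fall short. The weakness is mainly in sensitivity; on specificity only M184V is clearly thin. V106M cannot be judged, because no frequency is given.

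The size rests on these assumptions: the 2013 frequencies still apply, there is one sample per child, no tests are indeterminate or failed, and Illumina sequencing adds few positives to those found by consensus sequencing. Failed tests and the retrospective/prospective split would lower the counts per estimate. Reference laboratory samples would raise them.

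A reader might also conclude that the claim should rest on class-pooled results or on a strict lower-limit test. Neither is a clear gain: pooling can hide a failing rare codon, and the strict test would usually fail a good assay at these counts.

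**What to change.** In protocol section F (Aim 2b), and in an OLA Simple section added to the SAP:

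- Report each codon's sensitivity and specificity with the number of positives and negatives and exact two-sided 95% confidence intervals.
- Make the >90% claim for a measure at a codon only where there are at least 36 relevant results (positives for sensitivity, negatives for specificity), and always show the interval with it. Thirty-six is a floor below which the claim cannot be supported, not a powered sample size.
- Report all other codons descriptively, including PI codons with few or no positives.
- Class-pooled results may be added but must not replace codon results.
- State the number of reference laboratory samples, and choose them from those already sequenced so as to cover K65R, V106M and the PI codons.
- Take positive and negative predictive values from unselected study samples only.
- Note that choosing samples positive by consensus sequencing may favour high-frequency variants, since the protocol puts its detection limit at about 20% of the viral population against about 10% for OLA Simple.

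The cost is plan wording and a selection step for samples that already exist. The downside is fewer codon-level claims, and sensitivity from selected samples that applies mainly to variants that consensus sequencing detects.

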
## **G. Summarize Knowledge to be Gained**

The findings from this pilot study will inform programmatic scale-up of POC VL and DRM testing in Kenya and elsewhere. Additionally, our findings will provide crucial HIV drug resistance information for children on ART, which is currently lacking and very likely to undermine current management approaches for children with virologic failure. Specifically, data collected from this study will help optimize future POC VL and DRM testing strategies. This work will directly inform national policy approaches to ART regimen choices for children in Kenya. Children living with HIV have continually lagged adults regarding

HIV treatment access and health outcomes including viral suppression; our study strives to contribute to the evidence-base that will close this gap.

## HUMAN SUBJECTS PROTECTIONS

Ethical approval for this study will be obtained from all relevant institutional review boards before initiating any of the study data collection activities. In the US, UW and UCD's Institutional Review Boards will review this protocol. UCSF already has ethical approval from both UCSF and CDC for routine data collection and evaluation at FACES sites in Kenya that will be facilitated through UCSF. In Kenya, the protocols will be reviewed by AMREF IRB. We will ensure that all procedures conform to US, Kenyan, and international ethical standards regarding research involving human subjects. Future studies or analyses conducted with the data collected in this study will undergo separate ethical reviews.

The proposed research will be conducted in collaboration with Family AIDS Care and Education Services (FACES), a CDC/PEPFAR-funded HIV prevention, care, and treatment program operating in western Kenya since 2005, which already has long-standing positive relationships with the local Ministry of Health (MOH) and the study communities. Our study design takes advantage of the extensive existing infrastructure of FACES and current laboratory infrastructure. Additionally, the feasibility, acceptability and potential for scale up of the proposed interventions were carefully considered with MOH and FACES investigators. The proposed research builds on our findings and our experience protecting human subjects in the proposed study regions gained during the implementation and operational research by FACES such as the Rapid Results Initiative for PMTCT as well as the MOTIVATE Study (Mother and Infant Visit Adherence and Treatment Engagement Study) for which [name] is a multiple-PI (NICHD 1R01HD080477-01).

